After the subject-specific FHO is ready, the stroke participant and his/her paired PT will be called to participate the 1st and 2nd lab-based training with ReIn-hand device. During these 2 visits, the assigned PT (1st test) or the research PT (2nd test) will train the stroke participant to use his/her FHO and the ReIn-Hand software on a mobile phone, until the stroke participant demonstrates the ability in using the device independently twice in a row. On the 2nd test, the research PT will also re-test partial of the clinical assessments, however, this time with the assistance of ReIn-Hand device. Each of these 2 visits is expected to last about 3 hours. During these 2 visits, we will measure the time for a stroke participant to learn the use of ReIn-Hand device. Within 0-3 days after the 1st (for PTs) or the 2nd lab-based training (for individuals with stroke), a 5min user survey to report the level of ease-of-use of the ReIn-Hand device will be conducted.

[figure not shown]

Figure 4. EEG Experimental setup showing a subject using the ACT^{3D} robot while high-density EEG and surface EMG signals will be simultaneously recorded. Visual feedback will be displayed on a computer screen.

F.2. Home-based practice

After the 3 lab-based visits as listed above, 4 out of 20 stroke participants will further participate the home-based practice. They will take the ReIn-Hand device, including his/her FHO, the mobile phone with ReIn-Hand software, and the electronic stimulator (300 PV, Empi, Minnesota, USA, a FDA approved clinical device) back to home. At home, they will perform 20 trials of pre-set tasks, like reaching and grasping, per session (1 hour), 1 session per day, 7 days per week for 12 weeks. During these 12 weeks, they will visit the lab once per week to make necessary device changes, update the partial of the clinical assessments, all without ReIn-hand. These clinical tests will also be re-measured at 1 and 3-month after the home-based practice, again without ReIn-hand.

Both electrodes and electrical stimulator are commercially available devices (300 PV Complete Electrotherapy System, Empi, Inc., St. Paul, MN). Each subject will be assigned task-specific, functional exercises targeted to their individual abilities, deficits, and personal preferences. Stimulation will be provided with the following characteristics:

Amplitude – at motor threshold with the maximum intensity lower than 100 mA
 Frequency – $50\pm20\%$ Hz

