 Pulse Duration – 300-400 microseconds
 Ramp/Fall Times and Duty Cycle – adjusted to the task

F.3. Data collection and procession

Main data collection is listed in table 2.

Day 1	#1, Demographic data, #2, Clinical assessments as listed above, #3, Time for a) determining the stimulation /recording electrode positions, b) for scanning,
Day 2	#1, EEG data, #2, EMG data, #3, finger position during hand-opening and graping force data during closing
Day 3	#1, Time for the stroke subject to a) to attach the FHO, b) use the software, including connecting all the cables following the instructions, c) set up the detection rule, and d) clean up. #2, The accuracy in detecting grasping and releasing; and #3, EMG data while performing task, sampled at 1K Hz.
Day 4	Measures #1-3 on Day 2, #4, ARAT and BBT with the assistance of ReIn-Hand.
Home-based test	Measures #1-4 on Day 3 and MAL-14, NSA, and hand opening and closing ability weekly during the 12-week home-based practice, then again at 1 and 3-month after. To the end of the 12-week home-based practice, we will use a GLOC scale (one question survey) to collect user overall satisfiaory level of the ReIn-Hand supported home practice.

Data analysis for evaluating the engineering aspects is listed on Table 3.

Primary measures	Measured by	Expectation
Time for learn-to-use the device	#1 on Day 3 and Day 4	<3 hours in each of the 2 days, and no difference between 2 days ¹ .
Time for setup and cleanup	#1 a) and d) on Days 3 & 4, and during the home-based test	<5 min for each, and significantly less than the

		measure #3 (a) on Day 1
Successful rate on controlling grasping and releasing during reaching	#2 on Days 3, 4, and during the home-based test	a false 'transfer' < 10%
Time delay caused by the device	We will detect the onset of EMG at the extensor measured on days 3 &4, and the onset of stimulation artifact. The latency between them will be calculated.	<350 ms
Difference in Clinical assessments with and without ReIn-Hand	Difference between measure #4 on Day 4 & measure #2 on Day 1	ARAT and BBT with ReIn-Hand will outperform that without ReIn-Hand.
Willingness to use ReIn-Hand at home	#1-3 during the home-based test	Continuous use on daily base.

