Cortical activity related to hand open with and without lifting	We will use EEG data to estimate the cortical activity related to the 2 motor tasks pre- and post-home-practice	Post-intervention cortical activity related to these 2 motor tasks become 'closer to' that in healthy control subjects.

¹Ease-of-use feature of the device will be reflected by the <3 hours learning time. We will further study effects of 1) PT's experience with ReIn-Hand, and 2) the number of experimental sessions on the time to learn to use the device. For PT's experience, since [name] already has 4-year experience in using current ReIn-Hand device in stroke participants, we will compare 1) the learning time on day 2 of the group 1 (N=10) working with the 10 PTs versus the time of the group 2 (N=10) working with [name]; and 2) the learning time of group 1 on day 2 with the 10 PTs versus the time of the same group on day 3 with [name]. A non-significant difference for both comparison will suggest non-significance for PT's experience in using the device. For the number of sessions needed to learn to use the device, we will compare the learning time of both groups on day 2 versus that on day 3. A non-significant difference will suggest sufficiency of one session in learning the device.

Evaluation of the usability of the ReIn-Hand: Within 0-3 days after Day 3, the 10 PTs and the 20 stroke participants will finish a 5min user survey to report the level of ease-of-use of the ReIn-Hand device. Items that will be rated (on ordinal scale 0-5, with the easiest use at 5) include: 1) determination of the stimulation/recording electrode positions (PT only), 2) setting up the initial detection rule (PT only), 3) fine adjustment of the detection rule (both), 4) placement of the FHO (both), 5) using the mobile phone software (both), 6) performance of the trained functional task (both). We expect to observe users' grades $\geq 4/5$, with grades $\leq 3/5$ will be queried for explanation and compiled for future design modifications.

Transportation: Participants will be given reimbursement for transportation expenses. Participants are encouraged to take public transportation, or to drive and park in Northwestern Medical School parking lots (located at [name] or [name]) where a parking sticker

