Official Title of the Study: Development of a FES Device for Hand Use During Arm Activities Following Stroke

NCT03986216

October 26, 2020

For each of the surveyed questions (scaled from 1-5 with 1 representing the no satisfied and 5 as very satisfied), we will calculate the mean and standard deviation, with a focus on identifying scores < 3/5.

We will use single and paired T-tests to determine the effects of PT experience and the number of training sessions on participant satisfaction, respectively.

We will use the repeated measure of ANOVA to test whether the training session number plays a role in the hand function as primarily measured by Box and Blocks Test and the other secondary measures.

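### Stroke participants are surveyed only after the research PT has trained all of them, which dilutes the SAP's test of PT experience on satisfaction and leaves its paired test on sessions without a second rating

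*Protocol*

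**What the plan says.** Protocol F.1.2 describes two lab training visits. On who trains, it says "the assigned PT (1st test) or the research PT (2nd test) will train the stroke participant". On the survey, it says "Within 0-3 days after the 1st (for PTs) or the 2nd lab-based training (for individuals with stroke), a 5min user survey". PTs are therefore asked after the first training and stroke participants after the second.

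F.3, under the usability evaluation, gives one time for both groups: "Within 0-3 days after Day 3, the 10 PTs and the 20 stroke participants will finish a 5min user survey".

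The visit numbering is not uniform:
- In Table 2, Day 2 is the EEG visit ("1, EEG data, #2, EMG data, #3, finger position during hand-opening"). Day 4 includes "ARAT and BBT with the assistance of ReIn-Hand", which F.1.2 places at the second training ("On the 2nd test, the research PT will also re-test partial of the clinical assessments"). The trainings are thus Days 3 and 4.
- Footnote 1 to Table 3 calls them days 2 and 3. It compares "the learning time of group 1 on day 2 with the 10 PTs versus the time of the same group on day 3 with" the research PT.

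The SAP plans single and paired t-tests, respectively, to "determine the effects of PT experience and the number of training sessions on participant satisfaction". It does not name the survey or the time at which the rating is taken.

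**The concern.** Footnote 1 defines the PT-experience groups: ten participants who start with the clinical PTs and ten who start with the research PT. F.1.1 assigns the first trainer at random, so a fair comparison is available after the first training. Under F.1.2 the participants are not asked then. They are asked after a second session that the research PT gives to everyone, when the clinical-PT group has also received the comparator.

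Any true difference would be understated. Footnote 1 takes a non-significant difference in learning time as a sign that PT experience does not matter. If satisfaction were read the same way, the survey's timing would itself favour that conclusion.

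The second half of the SAP sentence, on number of sessions, needs a rating after each session from the same person. F.1.2 supplies one rating. Those running the study also cannot tell from F.1.2 and F.3 together when each group is to be surveyed.

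**Working it through.** The plan states no effect size, power or alpha for this comparison, so there is no figure of its own to reproduce.

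**1. What the between-group test estimates.** I read the SAP's single t-test as the unpaired comparison of the two groups. Let δ be the effect on the rating of having the research PT rather than a clinical PT. Let w be the weight a participant gives to the first visit and 1 − w the weight given to the second.

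- Survey after the second visit: group 1 (clinical PT, then research PT) has expected rating μ + (1 − w)δ. Group 2 (research PT twice) has μ + δ. The difference is wδ.
- Equal weights, w = 0.5: difference 0.5δ.
- Latest visit only, w = 0: difference 0.
- Survey before the second visit: only one visit exists, so w = 1 and the difference is δ.

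The documents give no basis for choosing w.

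**2. Illustration of the cost.** Inputs: 10 versus 10 (footnote 1). Two-sided alpha 0.05 and effects in SD units are my assumptions. Power comes from the non-central t distribution with 18 degrees of freedom and non-centrality d√(10/2).

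| Share of the effect remaining | True effect 1.32 SD | True effect 1.0 SD |
|---|---|---|
| 100% | 0.800 | 0.562 |
| 75% | 0.557 | 0.355 |
| 50% | 0.289 | 0.185 |
| 25% | 0.108 | 0.083 |

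**3. The paired test.** With one rating per participant there are no pairs. If ratings were taken after both visits, let s be the effect of a second session. The change from first to second rating is s + (1 − w)δ in group 1, where the trainer changes, and s in group 2, where the trainer does not. Pooling 10 and 10 gives s + (1 − w)δ/2: s + δ/4 at w = 0.5, and s + δ/2 at w = 0. The pooled change mixes session and trainer; group 2 alone gives s.

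**4. Survey timing, side by side.**

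| Numbering | First training | Second training | F.3 survey falls after | Against F.1.2, participants (after second) | Against F.1.2, PTs (after first) |
|---|---|---|---|---|---|
| Table 2 | Day 3 | Day 4 | first training | conflict | agree |
| Footnote 1 | Day 2 | Day 3 | second training | agree | conflict |

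F.1.2 gives two times and F.3 gives one, so neither numbering reconciles them for both groups.

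**The case against.** **The timing for stroke participants may not conflict.** A reader using Table 2 might infer that F.3 plainly contradicts F.1.2 for them. The documents do not settle that. Footnote 1, which precedes the survey sentence, makes Day 3 the second training. Other text fits that numbering: Table 2's Day 4 row repeats measures from Day 2, although Table 3 takes learning time from Days 3 and 4; the home-based row cites four measures on Day 3, where Table 2 lists three; and F.2 counts three lab visits, which leaves out the EEG visit. This stands. It moves the conflict to the PTs and does not remove it.

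**The survey rates the device.** Its items cover detection-rule adjustment, orthosis placement, phone software and task performance. Asking after full training is reasonable for that purpose, and low scores feed design changes. This also stands, and is a reason to keep a rating after the second visit. It does not make that rating suitable for comparing trainers.

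**The main PT-experience contrast is safe.** Footnote 1 compares the groups' learning time at the first training, before the research PT has trained group 1. That is correct, and the present point does not touch it.

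**The test would be weak anyway.** With 10 versus 10, even undiluted data need about 1.32 SD for 80% power under the assumed alpha. In addition, F.1.2 trains everyone to the same standard of independent use, which may narrow differences already at the first visit. Both are fair; neither is a reason to accept further, avoidable dilution.

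**Conclusion.** Under F.1.2 the SAP's between-group test of PT experience on satisfaction is diluted toward no difference, and its paired test on number of sessions has no second rating. A non-significant result would not show that PT experience is irrelevant to satisfaction.

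A reader might go further and conclude that the comparison is void. The documents do not support that: the first trainer is randomly assigned and still differs between the groups, so whatever persists from the first session can be seen. The surviving share is unknown: half under equal weighting, none if only the latest visit counts. The power figures are illustrations, not estimates.

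The conclusion assumes that the SAP's satisfaction score is the protocol's ease-of-use survey. The scales differ (1-5 against 0-5), but the only other survey described, the one-question GLOC, reaches just the 4 home-practice participants. The timing conflict between F.1.2 and F.3 is certain for one of the two groups; which one depends on the numbering used.

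**What to change.** - Use one visit numbering in F.1.2, Table 2, footnote 1 and the rest of F.3, and state one survey schedule for PTs and one for stroke participants.
- Give each stroke participant the five-minute survey within 0-3 days after the first training and always before the second, and again within 0-3 days after the second.
- In the SAP, name this survey as the satisfaction measure and reconcile its scale with the protocol's. Use the first rating for the between-group test of PT experience, and both ratings for the paired test on number of sessions.
- When reporting the paired test, state that in group 1 the second session also brings a change of trainer, and show group 2 separately as the cleaner session effect.

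The cost is wording changes in both documents and one additional five-minute survey per stroke participant (20 in all). The second training visit must also not begin until the first survey is complete.

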We plan to recruit about 100 moderately to severely impaired stroke subjects who have some shoulder and elbow control, but lack hand function (UE FMA Scores of 10-40/66, CMcM \leq 4) to participate in the cross-sessional experiments. Individuals with stroke will be selected from the Clinical Research Registry (CRR) housed at the ShirleyRyan AbilityLab which contains more than 700 members, as well as from stroke survivors residing in the Chicagoland area who wish to participate in the study. Recruitment of subjects who are currently enrolled in the Clinical Research Registry will be done via phone call and email. Recruitment of stroke survivors residing in the Chicagoland will be done via flyer or on-clinical-site survey for willingness of participation. In addition, in order to facilitate recruitment, we will post this study on The New Normal (TNN¹) Match matchmaking portal, a National Institutes of Health (NIH) funded collaborative project to give communities access to information about healthy research opportunities. These stroke subjects will go through 1 or 2 stages (i.e., the 1st stage as remote prescreening which is optional and the 2nd one as on-site screening for eligibility test which is required) of eligibility tests. Recruitment for stroke participants will be ended when 20 individuals with moderate to severe impairment post-stroke are enrolled and finished the data collection.

Once confirmed their desire and willingness to participate, the potential participant will be asked to sign an online e-Consent form, or a hard copy consent form. For individuals who signed the e-Consent form and passed the remote pre-screen, a hard copy of consent form will still be signed on the first on-campus visit.

We will recruit 10 healthy individuals at least 45 years old. These individuals will participate in one session of the EEG experiment, and will provide control data to compare against the stroke individuals who partake in the home-based practice.

¹ <https://www.nucats.northwestern.edu/news/2020/northwestern-new-normal-launch.html>.

Also, 10 independent physical therapists (PTs) or senior physical therapy students (SPTs), who have experience working with stroke subjects and using FES, will be recruited for setting up the ReIn-Hand device for stroke users, and then teaching stroke users to use the device. Stroke, PT and SPT users will provide feedback from clinicians and stroke users' angles, respectively.

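### Table 3's primary measure of willingness to use the device at home is observed only in the 4 of 20 who have already agreed to home practice, so it measures adherence among those who agreed

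*Protocol*

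**What the plan says.** In protocol section F.3, Table 3 includes "Willingness to use ReIn-Hand at home" under its primary measures. The source given is items "1-3 during the home-based test" and the expectation is "Continuous use on daily base". No proportion, threshold or denominator is attached.

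Who reaches the home phase is set in section F.2. "After the 3 lab-based visits as listed above", "4 out of 20 stroke participants will further participate the home-based practice". The schedule there is "1 session per day, 7 days per week for 12 weeks", with a weekly lab visit. Section E fixes the stroke sample: "Recruitment for stroke participants will be ended when 20 individuals with moderate to severe impairment post-stroke are enrolled and finished the data collection".

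Two other instruments ask for users' views. The short survey described below Table 3 goes to all 20 stroke participants. Its six listed items concern ease of use, and none asks about taking the device home. The other is a single satisfaction question in Table 2: "To the end of the 12-week home-based practice, we will use a GLOC scale". It is asked only of those who complete home practice.

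The SAP covers survey scores, tests on satisfaction, and a repeated-measures analysis of hand function. It contains no analysis of willingness and no count of offers or refusals.

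**The concern.** Nobody can be observed using the device at home without first agreeing to take it home. Agreement to the 12-week programme is therefore a condition for entering the sample in which willingness is judged. The other 16 participants contribute nothing to the row, and anyone who was asked and declined would leave no trace in it.

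The measure also does not match its label. Daily use is prescribed by the protocol and supported by weekly visits, so what is seen is compliance with a schedule. Items 1 to 3 of the home test, as defined for Day 3 in Table 2, are handling times, detection accuracy and EMG. None is listed as a count of days used.

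Home use is the purpose of Objective 1, so readers are likely to take this row as evidence that stroke users want the device at home. Full adherence in four people who agreed would not show that.

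**Working it through.** The documents give no sample-size or precision calculation for this outcome, so there is no planned figure to reproduce beyond the count 4/20 = 20%. The remaining 16/20 = 80% are unobserved on this measure.

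**Inputs.** Four home participants out of 20 (F.2, E); 7 × 12 = 84 scheduled home sessions (F.2). The number offered home practice is not stated, so it is varied below as an assumption.

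**Step 1: the best possible result taken at face value.** If all four use the device daily, the result is 4/4. The exact (Clopper-Pearson) 95% lower limit is 0.025^(1/4) = 0.398. Perfect adherence would thus exclude only true rates below about 40%, even if the four were an unselected sample.

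**Step 2: the same result with refusals in the denominator.** With r refusals, the proportion is 4/(4 + r):

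| Assumed refusals | Accepted and used daily / offered | Proportion | Exact 95% interval |
|---|---|---|---|
| 0 | 4/4 | 100% | 39.8% to 100% |
| 4 | 4/8 | 50% | 15.7% to 84.3% |
| 8 | 4/12 | 33% | 9.9% to 65.1% |
| 16 | 4/20 | 20% | 5.7% to 43.7% |

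With offers and refusals unrecorded, every row of this table would appear as 4/4.

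**Step 3: is it the small number or the missing denominator?** Suppose k of the 20 are willing, four are drawn at random from all 20, every refusal is counted, and a willing person uses the device daily. The chance of 4/4 is then C(k,4)/C(20,4), with C(20,4) = 4845:

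- k = 4: 1/4845 = 0.02%
- k = 8: 70/4845 = 1.4%
- k = 10: 210/4845 = 4.3%
- k = 15: 1365/4845 = 28.2%

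If instead the four are simply people who agreed, 4/4 can be obtained whenever at least four of the 20 are willing. The possible distortion therefore comes from conditioning on agreement without counting refusals. The small number adds imprecision on top.

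**Step 4: precision if all 20 are asked.** Exact 95% intervals for yes/20 would be 27.2% to 72.8% at 10/20, 50.9% to 91.3% at 15/20, and 83.2% to 100% at 20/20.

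**The case against.** The strongest reply is that the documents describe no biased selection. They give a number, four, which may simply be fixed by design. A reader might infer from the timing, after staff have watched each person learn the device, that favourable participants are picked. Nothing in either document says so, or says that anyone is asked and declines. This stands: the bias is possible, not shown.

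A reader might also infer that the other 16 refused and that true willingness is 20%. That does not follow, because people who are never offered home practice are not refusers. The 20% is a worst-case bound. The documents do not plan to report a proportion either; 4/4 is the natural summary of the row, not a stated one.

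Nor is the result settled once the four are known. Someone who agrees at the start can stop during the 84 sessions. Agreement favours the expected result without guaranteeing it.

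The spill-over to other measures is limited. Set-up and clean-up time and detection accuracy are also measured on Days 3 and 4 in the lab, so only their home component depends on the four. The EEG comparison is within person, so selection there affects generalisability only.

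Finally, Table 3 is presented as an engineering evaluation, a four-person home phase is reasonable in device development, and low ease-of-use grades from all 20 are followed up. All fair. But ease of use is not willingness, and none of these points removes the dependence of the row on prior agreement.

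**Conclusion.** The point holds in limited form. The Table 3 row observes adherence to a prescribed schedule in four people who agreed to it, and 80% of the stroke sample is silent on the measure. Complete adherence would read as 4/4, with a lower limit of about 40%, and could correspond to anything from 100% down to 20% of those offered. That range rests on an assumed 0 to 16 refusals, since the number offered is not documented, and on all four using the device daily. The conclusion that the label and the measure differ needs neither assumption, and it holds however the four are selected. It is a change worth making because it is cheap; it does not invalidate the home phase as a pilot.

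**What to change.** 1. Add one item to the existing 5-minute survey, after the second lab training, asking all 20 stroke participants whether they would take the device home for the 12-week practice (yes/no and main reason). Report stated willingness as yes/20 with an exact 95% interval. F.1.2 and the usability paragraph below Table 3 describe the survey's timing differently, so align them at the same time.
2. State how the four are chosen: a random draw from those who are willing and eligible. Log every offer, refusal and reason.
3. Relabel the Table 3 row as adherence among the four, and base it on a recorded count of days used out of the 84 scheduled.
4. Add both summaries to the SAP. Note that the home component of set-up time and detection accuracy, and the pre/post EEG comparison, come from willing participants only.

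The cost is one survey question, a simple draw and a log, with no extra visits or participants. There are downsides. The new item records stated intention rather than behaviour. The home data will still come only from willing people. Home results may look slightly less favourable than under a less formal choice.

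### Table 3 takes the primary learning-time measure from the time to perform operating steps, while F.1.2 trains to independent use twice in a row; the two must be reconciled

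*Protocol*

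**What the plan says.** **Training rule (protocol F.1.2).** At each of the two lab training visits the participant is trained "until the stroke participant demonstrates the ability in using the device independently twice in a row". The section adds that the time taken to learn the device will be measured at both visits, and that each visit should last about 3 hours. It gives no start or stop point for the learning time. It also gives no rule for a participant who does not reach the criterion within the visit.

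**Source of the measure (F.3, Table 3).** The learn-to-use row is the first primary measure. Its source is item number "1 on Day 3 and Day 4" and its expectation is "<3 hours in each of the 2 days, and no difference between 2 days".

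**What that item contains (F.3, Table 2, Day 3).** Item number "1, Time for the stroke subject to a) to attach the FHO, b) use the software, including connecting all the cables", followed by "c) set up the detection rule, and d) clean up".

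**Other uses of the same item.** The set-up and clean-up row of Table 3 takes its data from item number "1 a) and d) on Days 3 & 4, and during the home-based test", with an expectation of under 5 minutes for each.

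**Day 4 (Table 2).** The entry is "Measures #1-3 on Day 2, #4, ARAT and BBT with the assistance of ReIn-Hand". Item 1 on Day 2 is EEG data.

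**Use of the result (footnote 1 to Table 3).** A learning time under 3 hours is taken as the sign of ease of use. Learning time is also compared by therapist experience and between the two training days. Non-significant differences are to be read as no effect of therapist experience and as one session being enough.

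**SAP.** It applies t-tests for therapist experience and session number to participant satisfaction. It neither defines nor analyses learning time.

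**The concern.** Time to reach competence and time to perform a task are different quantities. F.1.2 describes the first. The item that Table 3 points to reads as the second. No item in Table 2 records when the twice-in-a-row criterion was met, or whether it was.

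Three conclusions rest on this measure: ease of use, no effect of therapist experience, and sufficiency of one session. If the database is built from Tables 2 and 3, all three would be drawn from step times. A participant who never became independent could still have step times adding up to well under 3 hours, and would count as meeting the expectation.

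**Working it through.** The documents give no power or sample-size calculation for this measure, so there is no figure to reproduce. The check traces the cross-references and then bounds the target.

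**1. Does item 1 mean training time or step time?**
- It is worded as the participant's time for four operations: a) attaching the orthosis, b) using the software, including cabling, c) configuring the detection rule, d) cleaning up.
- Components a) and d) are reused in Table 3 as set-up and clean-up times, expected under 5 minutes each. That is a performance time.
- The same item is collected again weekly during the 12 weeks of home practice, after both training visits. Time to learn would not sensibly recur each week; time to perform a step would.

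The step-time reading is therefore much the more natural one.

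**2. What does the target then test?**
Inputs: limit 3 h × 60 = 180 min (Table 3); a) and d) at their expected ceiling of 5 min each (Table 3).

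Time that b) and c) must take for the total to reach the limit = 180 − 5 − 5 = **170 min**.

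A second bound assumes that two complete uses fit into one visit of V minutes, so that one use takes at most V/2. F.1.2 gives V as about 180; the other values are assumptions.

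| Visit length V (min) | Longest single use, V/2 (min) | Below 180? |
|---|---|---|
| 150 | 75 | yes |
| 180 | 90 | yes |
| 210 | 105 | yes |
| 240 | 120 | yes |

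For a single use to reach 180 min, the visit would have to last at least 2 × 180 = 360 min, with no time for instruction.

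**3. What if time to criterion was intended?**
The visit is expected to last about 180 min, the same as the limit. A failure would then appear mainly as a participant who had not reached the criterion when the visit ended. The plan has no field for that and no rule for counting it.

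**4. Does Day 4 supply a time?**
Table 3 needs item 1 on Day 4. Table 2 defines Day 4 by reference to Day 2, whose item 1 is EEG data, so read literally there is no Day 4 time. A numbering slip is likely:
- Footnote 1 calls the two training days day 2 and day 3.
- The home-based row of Table 2 cites four measures on Day 3, where only three are listed.

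Both fit an EEG day having been placed second without the later references being renumbered. That is an inference, but the between-day comparison depends on the correct reference.

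**The case against.** The strongest reply is that the protocol does commit to measuring learning. F.1.2 says so directly after stating the criterion, and footnote 1 speaks of learning time throughout. Table 2 is introduced as the main data collection, so absence from it does not prove that a time goes unrecorded. The learn-to-use row cites item 1 as a whole and only for the training visits, which could mean time spent learning the four operations. The 3-hour figure also suits a training session: section D reports that all 8 preliminary participants learned the platform within one session of that length.

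Much of this stands. A reader might infer that learning will not be measured at all, or that the under-3-hours target is certain to be met. The documents support neither. The first runs against F.1.2. The second needs the step-time reading and actual times for b) and c), which are not given; the 5-minute values for a) and d) are themselves expectations under test.

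The reply does not remove the conflict. The 5-minute targets and the weekly home collection fit poorly with a training-time reading of item 1. F.1.2's commitment has no start, no stop and no corresponding item in Table 2.

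A further objection is that changing the source alone leaves the target weak, because the visit is about as long as the limit. That is correct, and is why a rule for non-achievers is needed.

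**Conclusion.** The point holds as an unresolved conflict that leaves the first primary measure without a usable definition. Table 3's stated source does not measure learning against the F.1.2 criterion, and footnote 1 draws its conclusions from a learning time that neither table records.

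If Table 3 is followed, the under-3-hours target says little about learning: b) and c) would need 170 of the 180 minutes for it to be missed. This rests on the step-time reading, on one performance of each step, and on a) and d) being at their 5-minute ceiling. If F.1.2 is followed instead, the target roughly equals the visit length, and the informative result is whether the criterion was reached, which is not recorded. The Day 4 pointer is a separate error of reference in the same chain.

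This should be corrected before the data are analysed, because it decides what the ease-of-use, therapist-experience and one-session conclusions rest on.

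**What to change.** 1. Add to Table 2, for both training visits, the minutes from the start of training to completion of the second consecutive independent use, with a yes/no field for whether that criterion was reached.
2. Point the learn-to-use row of Table 3 and footnote 1 to this new item. Keep item 1 for step, set-up and clean-up times.
3. Count a participant who does not reach the criterion within the visit as not meeting the under-3-hours expectation. Treat that time as censored at the end of the visit in the footnote 1 comparisons, using a method that accepts censored times. Report the proportion reaching the criterion at each visit.
4. Correct the Day 4 cross-reference in Table 2 and the day numbering in footnote 1, so that both name the two training visits.

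The cost is one timed interval and one field per training visit, plus changes to table wording. The reported learning times will look longer than step times would.
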